#### 3.2.2.1 Adverse events

Adverse events will be coded initially using the Medical Dictionary for Regulatory Activities (MedDRA) Version 21.0 and updated regularly.

Listings will be presented and sorted by cohort and within cohort sorted by cancer type for phase I and by cancer type for phase II, with subject id, start time of AEs, primary system organ class, preferred term and verbatim text for all adverse events recorded during the study. Listings sorted by primary system organ class, preferred term, verbatim, subject id, start time of AEs may be also required.

Listings of serious adverse events (SAE), adverse events leading to discontinuation of study treatment and listings of deaths will also be presented.

Treatment Emergent Adverse Events (TEAE) will be flagged (\*) in the adverse events listing and will be summarised.

A TEAE is defined as any AE that occurs during the active phase of the study if:

- It was not present prior to receiving the first administration of Lu-OPS201; or
- It was present prior to receiving the first administration of Lu-OPS201 but the intensity increased during the active phase of the study; or
- It was present prior to receiving the first administration of Lu-OPS201, the intensity is the same but the drug relationship became related during the active phase of the study.

A Ga-OPS202 TEAE is defined as any AE that occurs if:

- It was not present prior to receiving the administration of Ga-OPS202; or
- It was present prior to receiving the administration of Ga-OPS202 but the intensity increased after the administration of Ga-OPS202; or
- It was present prior to receiving the administration of Ga-OPS202, the intensity is the same but the drug relationship became related after the administration of Ga-OPS202.

TEAE period for Ga-OPS202 will be from the administration of Ga-OPS202 to one day after the administration. All Ga-OPS202 TEAE will be summarized together.

An overall summary table of all adverse events will be presented, which will summarise the following information:

- Any TEAEs,
  - Lu-OPS201-related TEAEs,

SAP Final: Version 2.0: [03 January 2020]

43/57

- $^{68}\text{Ga}$ -OPS202-related TEAEs,
- OPS301-related TEAEs,
- NCI CTCAE grade 3/4/5 TEAEs,
  - $^{177}\text{Lu}$ -OPS201-related NCI CTCAE grade 3/4/5 TEAEs,
  - $^{68}\text{Ga}$ -OPS202-related NCI CTCAE grade 3/4/5 TEAEs,
  - OPS301-related NCI CTCAE grade 3/4/5 TEAEs,
- DLT TEAEs,
- Deaths due to TEAEs,
- Treatment-emergent SAEs,
  - $^{177}\text{Lu}$ -OPS201-related treatment-emergent SAEs,
  - $^{68}\text{Ga}$ -OPS202-related treatment-emergent SAEs,
  - OPS301-related treatment-emergent SAEs,
- Discontinuation of study treatment due to TEAEs,
  - Discontinuation of study treatment due to  $^{177}\text{Lu}$ -OPS201-related TEAEs,
  - Discontinuation of study treatment due to  $^{68}\text{Ga}$ -OPS202-related TEAEs,
  - Discontinuation of study treatment due to OPS301-related TEAEs,
- Dose reduction due to TEAEs,
  - Dose reduction due to  $^{177}\text{Lu}$ -OPS201-related TEAEs,
  - Dose reduction due to  $^{68}\text{Ga}$ -OPS202-related TEAEs,
  - Dose reduction due to OPS301-related TEAEs,
- Dose interruption due to TEAEs, and
  - Dose interruption due to  $^{177}\text{Lu}$ -OPS201-related TEAEs,
  - Dose interruption due to  $^{68}\text{Ga}$ -OPS202-related TEAEs,
  - Dose interruption due to OPS301-related TEAEs,
- Dose increased due to TEAEs, and
  - Dose increased due to  $^{177}\text{Lu}$ -OPS201-related TEAEs,
  - Dose increased due to  $^{68}\text{Ga}$ -OPS202-related TEAEs,
  - Dose increased due to OPS301-related TEAEs

Summary tables of adverse events will be provided with the number and percentage of subjects with adverse events classified by primary system organ class, preferred term (ordered alphabetically) and associated NCI/CTC worst grade. In the event of multiple occurrences of the same adverse events being reported by the same subject, the maximum intensity (Grade 5 > Grade 4 > Grade 3 > Grade 2 > Grade 1 > missing > not applicable) and the most serious causality (related) will be chosen. Maximum grade or severity will be tabulated by subject for each MedDRA SOC and PT. Analyses of AEs and SAEs may be performed: regardless of the relationship to the IIP/IRPP and related to the IIP/IRPP. Moreover, all AEs including SAEs and SAEs only will be tabulated.

$^{68}\text{Ga}$ -OPS202 TEAEs occurred during TEAE period for  $^{68}\text{Ga}$ -OPS202 will be summarized following the same manners and flagged in all adverse events data listings.

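### Minor: for repeated adverse events the SAP picks the worst grade and the worst causality separately, so related-by-worst-grade tables can show a related Grade 3+ event that no single episode was

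*SAP*

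**What the plan says.** The rule is in the paragraph of SAP section 3.2.2.1 on summary tables by system organ class, preferred term and worst grade. It applies "In the event of multiple occurrences of the same adverse events being reported by the same subject". Two things are then selected. The first is the grade, by a ranking from Grade 5 down to Grade 1, with missing and not applicable last. The second is the relationship to treatment, in these words: "and the most serious causality (related) will be chosen". The rule on grade is then carried into the tables: "Maximum grade or severity will be tabulated by subject for each MedDRA SOC and PT".

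Two planned outputs need grade and causality together:

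- The same paragraph allows analyses "regardless of the relationship to the IIP/IRPP and related to the IIP/IRPP". These are optional, and the order of filtering and collapsing is not given.
- The overall summary table, specified earlier in the section, has rows such as "OPS201-related NCI CTCAE grade 3/4/5 TEAEs", with matching rows for 68Ga-OPS202 and OPS301. No collapsing rule is stated for that table.

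Section 5 records that the study closed prematurely and that the Clinical Study Report analysis was revised. The adverse event outputs selected there are all listings.

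**The concern.** Grade and causality are attributes of one episode. Taking the maximum of each over several episodes can build a pair that no episode had. For an all-causality table this is harmless, because only the grade is used. For a table headed as related events by worst grade it is not, because the reader takes each entry to be an event of that grade that the investigator judged related.

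The wording also leaves two programmers free to report different counts from the same data. One collapses first and then selects related records; the other selects related occurrences first and then takes the worst grade. The text is closer to the first order but does not exclude the second. Nor does it say that causality is resolved separately for each of the three products. In a trial whose Phase I objective is safety and tolerability, the related Grade 3+ count should have one definition.

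**Working it through.** The SAP gives no figure for this point, so there is none to reproduce. The check applies the rule to an example, establishes the direction of error, and shows its size under stated assumptions.

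**Example.** Same preferred term, same subject: episode 1 is Grade 1, related; episode 2 is Grade 3, unrelated.

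| Reading | Kept for the related table | Counted as related Grade 3+ | Counted as related, any grade |
|---|---|---|---|
| Literal: maximum grade and worst causality taken separately | Grade 3, related | 1 | 1 |
| Keep related occurrences, then maximum grade | Grade 1, related | 0 | 1 |
| Keep the causality of the worst-grade episode | nothing (Grade 3, unrelated) | 0 | 0 |

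Only the second reading gets both counts right. The literal rule moves the subject from the Grade 1 column to the Grade 3 column; the any-grade related count does not change.

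**Direction.** If a subject has an occurrence that is both related and Grade 3+, then the maximum grade is at least 3 and the worst causality is related, so the literal rule counts that subject. It may also count subjects with no such occurrence. It can therefore overstate related Grade 3+ counts but cannot understate them.

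**Which pairs are affected.** With five grades and two causality values there are 10 possible episodes and 10 × 10 = 100 ordered pairs.

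- A pair that neither episode had arises when the unrelated episode has strictly the higher grade: 10 grade combinations × 2 orders = 20 of 100.
- A false related Grade 3+ needs a related episode of Grade 1 or 2 and an unrelated one of Grade 3, 4 or 5: 2 × 3 × 2 orders = 12 of 100.

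These are counts of combinations, not expected frequencies.

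**Size under assumptions.** Take subjects with exactly two episodes of a term, independent of each other, with grade and causality also independent. Let r be the probability that an episode is related and g the probability that it is Grade 3+. None of these inputs comes from the SAP.

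- True proportion: 1 − (1 − rg)²
- Literal rule: [1 − (1 − r)²] × [1 − (1 − g)²]

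| r | g | True | Literal rule | Ratio |
|---|---|---|---|---|
| 0.5 | 0.2 | 1 − 0.90² = 19.0% | 0.75 × 0.36 = 27.0% | 1.42 |
| 0.5 | 0.1 | 1 − 0.95² = 9.75% | 0.75 × 0.19 = 14.25% | 1.46 |
| 0.3 | 0.2 | 1 − 0.94² = 11.6% | 0.51 × 0.36 = 18.4% | 1.58 |

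**Dilution.** Subjects with a single episode of the term are not distorted. If a fraction f of the subjects in a table have two such episodes, the table-level excess in the three rows is f × 8.0, f × 4.5 and f × 6.7 percentage points. The SAP gives no basis for f.

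**Small cohorts.** Section 1.3.4 plans 3–5 subjects per Phase I cohort. One artificial case is 1/3 = 33.3% or 1/5 = 20.0% of a cohort, provided that the subject has no genuine related Grade 3+ occurrence counted in the same row.

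**The case against.** The strongest reply is that little depends on this rule. Most of that reply stands.

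- **Section 5 reduces the report to listings.** No overall summary and no worst-grade table is among the selected outputs, and listings show single episodes, which the rule does not touch. This stands and removes most of the practical consequence for this report.
- **The overall summary has no collapsing rule.** Its related Grade 3/4/5 rows can be counted directly as subjects with at least one event having both attributes. This stands. A reader might infer that those rows are necessarily inflated, but the SAP does not say that they are built from the collapsed records.
- **Related-only tables could be filtered first.** The wording permits it. That makes the result depend on an unstated order; it does not make the rule adequate.
- **The rule is cautious.** It cannot hide a related high-grade event. True, but the all-causality worst-grade tables already give the cautious view, and a related count should count events that occurred.
- **No decision rests on it.** A reader might infer that dose escalation or the MTCA could be distorted. The documents do not support that: the MTCA is defined from DLTs and organ absorbed doses (section 3.1.1), and DLTs have their own definition and individual listings (sections 1.3.2.2 and 3.2.2.3). Section 3.2.2 has toxicities tabulated for the data review board but does not say that those tables use this rule.

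**Conclusion.** The point holds as a minor defect in a written rule. Read literally, section 3.2.2.1 can show a related event at a grade that no related episode reached. This happens in related worst-grade tables by system organ class and preferred term, and in the overall-summary related rows only if those are built from the collapsed records.

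The direction is certain: related Grade 3+ counts can only be overstated. The size is not known. The ratios of 1.42 to 1.58 rest on two same-term episodes per subject and on independence, and apply to such subjects alone; they should not be read as inflation of the trial's related Grade 3+ rate. All-causality tables, the DLT listings and the listings selected in section 5 are unaffected. The defect matters for any adverse event summary table that is still produced.

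**What to change.** In section 3.2.2.1, replace the joint selection of grade and causality with a rule in two parts. All-causality tables take the maximum grade over all occurrences of the event in the subject. Related tables, and the related rows of the overall summary, first keep the occurrences judged related to the product concerned and then take the maximum grade among those, separately for 177Lu-OPS201, 68Ga-OPS202 and OPS301.

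The cost is one sentence in the SAP and a change in the order of two programming steps. No new data are needed, and the listings stay as they are.

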### 3.2.2.2 *Laboratory data*

Laboratory data must be listed in Standard International (SI) units and also be listed in local units.

A separate listing of normal ranges for SI units will be provided by gender and age where relevant.

Laboratory data will be listed in SI units and abnormal values will be flagged (High, [H], Low [L], clinically significant [C], NCI-CTC grade (G)) where applicable. Any unscheduled laboratory assessments will be flagged [U] in the listings.

A listing will be presented of all values for a subject with at least a clinically significant abnormal value.

Haematological and biochemistry toxicities will be recorded and graded according to the NCI-CTC criteria, version 5.0. The NCI CTC grade (0 to 4) of haematology and biochemistry by cycle and by subject and will be listed in the Section 16.2.8. Listings of the laboratory parameters in section 14.3.4 & 14.3.5 will include listings of NCI-CTC Grade 3 and 4 haematological toxicities, listings of NCI-CTC Grade 3 and 4 biochemical toxicities and listings of out of range biochemistry parameters that could not be graded using NCI-CTC grade (below LLN – normal – above ULN).

For white blood cells (WBC), neutrophils, platelets and haemoglobin, with associated grade 3 or 4 toxicities, nadir and day to nadir will be calculated (refer to Appendix 1, Derived data).

For categorical urinalysis data (normal/abnormal) frequency tables, by cohort and/or cancer type will be presented at each scheduled assessment as well as the change from baseline with the following categories: improved, stable, worsened and abnormal worsening. Shift tables may be presented for the number and percentage of subjects with [normal, abnormal].

For continuous urinalysis data, summary statistics, by -cohort and/or cancer type, will be presented at each scheduled assessment for actual values and changes from baseline.

### *3.2.2.3 Maximum Tolerated Single and Cumulative Activity*

Individual listings and treatment summaries of DLTs with CTCAE code and grade will be presented. The incidence of subjects with DLTs during Cycles 1 or 2 of the radioactivity escalation will be summarised by cohort and/or cancer type and, if possible, modelled as a function of the cumulative radioactivity for Cycles 1 and 2 using Bayesian logistic regression.

Details for the Bayesian logistic regression is described in a separate analysis plan and protocol Appendix 1.

### *3.2.2.4 Vital signs*

Vital signs will be listed at each assessment by cohort and/or cancer type and subject. Any unscheduled vital signs will be flagged [U] in the listing.

Baseline values will be defined as the last vital signs measurement collected prior to the first dose of study drug.

Summary statistics by cohort and/or cancer type will be presented at each scheduled assessment for actual values and changes from baseline.

For interpretation of clinical significance (normal / abnormal, not clinically significant / abnormal, clinically significant / not evaluable), a frequency table will be presented, by cohort and/or cancer type, at each post-dose assessment and for the worst value between post-dose assessments (abnormal, clinically significant > abnormal, not clinically significant > not evaluable).

### *3.2.2.5 ECG*

ECG results will be listed at each assessment by cohort and/or cancer type and subject. Any unscheduled ECG will be flagged [U] in the listings.

Baseline will be defined as the last ECG measurement collected prior to the first dose of study drug.

For continuous ECG parameters, summary statistics, by cohort and/or cancer type, will be presented at each scheduled assessment for actual values and changes from baseline.

For sinus rhythm, a frequency table by cohort and/or cancer type, will be presented at each scheduled assessment.

For interpretation of clinical significance (normal / abnormal, not clinically significant / abnormal, clinically significant / not evaluable), a frequency table will be presented, by cohort and/or cancer type, at each post-dose assessment and for the worst value between post-dose assessments (abnormal, clinically significant > abnormal, not clinically significant > not evaluable).

### 3.2.2.6 *Physical examination*

For physical exam assessments (abnormal, not clinically significant / abnormal, clinically significant /normal), a frequency table will be presented, by cohort and/or cancer type, at each post-dose assessment and for the worst value between post-dose assessments (abnormal, clinically significant > abnormal, not clinically significant > normal > not evaluable).

### 3.2.3 *Exploratory biomarkers*

- The association between the uptake on  $^{68}\text{Ga}$ -OPS202 PET/CT with sstr2 expression on tumours as determined by IHC will be explored.
- Immunohistochemistry staining of sstr2 of the primary tumour is defined by three parameters:
  - % of positive tumour cells (at the membrane compartment) ranging from 0% to 100%
  - Intensity of staining with score of 0, 1, 2 or 3
  - H score = % of positive cells  $\times$  Intensity of staining. H score ranges from 0 to 300.

$^{68}\text{Ga}$ -OPS202 PET/CT uptake will be measured by SUVmean at screening.

Pearson's correlation coefficient will be used to estimate the correlation between SUVmean and % of positive cells.

The correlations between SUVmean and the intensity of staining as well as between SUVmean and H score will be examined using Spearman's correlation coefficient.

Additionally, H score will be split into two categories as follows: negative if H score < 50 or positive if H score  $\geq$  50. As for SUVmean, a sample will be considered positive if SUVmean is > 0 and negative if SUVmean is 0.

H score (positive/negative) and SUVmean (positive/negative) will be described in a 2x2 table using descriptive statistics (frequencies and percentage).

Individual values of H score (positive/negative) and SUVmean (positive/negative) will be listed by subject.

- Change in renal biomarkers compared to baseline (Day 1) will be summarised descriptively.
- Change in pancreatic function biomarkers compared to baseline (Day 1) will be summarised descriptively.
- Change in testicular function biomarkers compared to baseline (Day 1) will be summarised descriptively.

- Change from baseline (Cycle 1 Day 1 before infusion) in DNA-DSB in peripheral lymphocytes, and DNA repair in blood and in tumour tissue will be summarised descriptively.
- Change from screening in tumour microenvironment, transcriptomics, and other disease markers of interest will be summarised descriptively.
- Germinal mutations in blood measured before infusion will be summarised descriptively.

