### **Pre-treatment Period**

A subject that qualifies will receive  $^{68}\text{Ga}$ -OPS202 and will be imaged on PET/CT. Subjects with at least two sstr2 avid lesions of  $\geq 20$  mm in the longest diameter on  $^{68}\text{Ga}$ -OPS202 PET/CT scan, confirmed by central read and having  $\geq 50\%$  matching between the lesions detected on  $^{68}\text{Ga}$ -OPS202-PET/CT and on  $^{18}\text{F}$ -FDG-PET/CT as confirmed by central reader will then be treated with  $^{177}\text{Lu}$ -OPS201.

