  - Correlation between the uptake of  $^{68}\text{Ga}$ -OPS202 in tumour lesions expressing sstr2 on PET/CT images and the uptake on  $^{177}\text{Lu}$ -OPS201 SPECT/CT.
  - Proportion of subjects with sstr2-positive tumour lesions by  $^{68}\text{Ga}$ -OPS202 PET/CT scans as assessed by the identification of avid lesions in subjects screened for  $^{177}\text{Lu}$ -OPS201 treatment at baseline.
  - Diagnostic sensitivity of  $^{68}\text{Ga}$ -OPS202 imaging using RECIST by subject-based analysis.
  - Diagnostic sensitivity of  $^{68}\text{Ga}$ -OPS202 imaging by using mGa-RECIST by subject-based analysis.
  - Diagnostic sensitivity of  $^{68}\text{Ga}$ -OPS202 imaging by subject-based, organ-based and lesion-based analysis compared to standard-of-truth (SOT) of ceCT (or ceMRI).
  - Diagnostic sensitivity of  $^{68}\text{Ga}$ -OPS202 imaging by both organ-based and lesion-based analysis compared to standard-of-truth (SOT) of  $^{177}\text{Lu}$ -OPS201 SPECT/CT.

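### PET positivity in the IHC comparison is cut at SUVmean above zero, and with no rule coding non-avid tumours as zero the PET-negative row of the 2×2 table is likely to be empty or nearly so

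*SAP*

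**What the plan says.** SAP Section 3.2.3 measures uptake as SUVmean on the screening 68Ga-OPS202 PET/CT. On the tissue side, "Immunohistochemistry staining of sstr2 of the primary tumour is defined by three parameters": percentage of positive cells, staining intensity, and their product, the H score. Pearson and Spearman correlations on continuous SUVmean come first.

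Both measures are then dichotomised. For tissue, "H score will be split into two categories as follows: negative if H score < 50 or positive if H score" is 50 or more. For the tracer, "a sample will be considered positive if" SUVmean is above 0, and negative if it is 0. The two classifications "will be described in a 2x2 table using descriptive statistics (frequencies and percentage"). No test is planned, and no analysis population is named for the table.

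Elsewhere positivity rests on avidity:
- **Section 1.2, Pre-treatment Period.** "Subjects with at least two sstr2 avid lesions of" at least 20 mm, confirmed by central read, may go on to treatment, subject also to at least 50% lesion matching with FDG-PET.
- **Section 2.2.3.** The 68Ga-OPS202 positive population needs at least one lesion identified by central readers on the screening PET.
- **Section 3.1.2, Phase II.** The proportion of sstr2-positive subjects is "as assessed by the identification of avid lesions in subjects screened for" treatment.

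**The concern.** The tissue axis has a working threshold on a 0 to 300 scale. The tracer axis has none, because any uptake above zero, however slight, counts as positive. A table of this kind exists to show discordance, above all tumours that are positive on IHC and negative on PET. If nothing can fall in the PET-negative row, those tumours cannot appear, and agreement reflects only how many samples pass the H-score cut.

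There is also an inconsistency. Section 1.2.1 treats a scan negative for sstr2 as a real screening outcome. Under Section 3.2.3 the same subject could be tabulated as PET-positive if any non-zero SUVmean is recorded for the tumour.

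**Working it through.** The SAP states no figure for this table, so there is none to reproduce beyond the scale. The maximum H score is 100 × 3 = 300, which agrees with "H score ranges from 0 to 300".

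**Inputs from the SAP**
- Phase I (Section 1.2.1): up to 30 treated, 55 to 60 imaged. Untreated: 55 − 30 = 25 to 60 − 30 = 30.
- Phase II (Section 1.2.1): about 172 treated, about 340 imaged. Untreated: 340 − 172 = 168.
- Screening biopsy mandatory (Section 1.3.2.9, Tumour Biopsy).
- Missing data not imputed, observed data only (Section 3.2.4.1).

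**Assumption.** The H-score-positive share is not in the SAP, so it is varied.

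**Formula.** Cells are a = PET+/IHC+, b = PET+/IHC−, c = PET−/IHC+, d = PET−/IHC−, with n the total.
- Raw agreement: po = (a + d)/n
- Chance agreement: pe = [(a + b)(a + c) + (c + d)(b + d)]/n²
- Kappa: (po − pe)/(1 − pe)

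If c = d = 0, then po = a/n and pe = n·a/n² = a/n. Kappa is therefore 0 for any a below n, and raw agreement equals the IHC-positive share.

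**Reading 1: treated subjects, classified at subject level.** Each has at least two avid lesions, so c = d = 0.

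| n | Assumed IHC+ share | (a, b, c, d) | po | Kappa |
|---|---|---|---|---|
| 30 | 50% | (15, 15, 0, 0) | 0.50 | 0 |
| 30 | 90% | (27, 3, 0, 0) | 0.90 | 0 |
| 172 | 50% | (86, 86, 0, 0) | 0.50 | 0 |
| 172 | 90% | (155, 17, 0, 0) | 0.90 | 0 |

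The same holds at subject level in the 68Ga-OPS202 positive population, because Section 2.2.3 requires a PET lesion.

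**Reading 2: all imaged subjects, every non-avid tumour coded 0, tissue available for all.** Phase I is illustrated with n = 57, split into 30 treated and 27 untreated.
- IHC+ share 90% in avid and 10% in non-avid: (27, 3, 3, 24). po = 51/57 = 0.895; pe = (30 × 30 + 27 × 27)/57² = 1629/3249 = 0.501; kappa = 0.79.
- IHC+ share 70% and 30%: (21, 9, 8, 19). po = 40/57 = 0.702; pe = (30 × 29 + 27 × 28)/57² = 1626/3249 = 0.500; kappa = 0.40.
- Phase II, n = 340, same two assumptions: (155, 17, 17, 151), kappa 0.80; and (120, 52, 50, 118), kappa 0.40.

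**Reading 3: the same subjects, with SUVmean taken from the tumour region and any non-zero value positive.** The first Phase I example becomes (30, 27, 0, 0). po = pe = 30/57 = 0.526; kappa = 0.

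Readings 2 and 3 use the same subjects and the same tissue results. Only the coding of non-avid uptake differs, and it moves kappa from 0.79 to 0. The SAP does not state that coding.

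**The case against.** A reader might infer something stronger: that eligibility makes every treated subject PET-positive by construction, so the table is degenerate whatever is done. The text does not support this, for two reasons.
- **Population.** Section 3.2.3 does not restrict the table to treated subjects. Uptake is measured at screening and the biopsy is mandatory at screening. About half of imaged subjects are expected to go untreated, so screen failures could supply PET-negative cases.
- **Unit of classification.** The rule classifies a sample, with IHC on the primary tumour. Eligibility concerns any two lesions and asks for only 50% matching with FDG-PET. A treated subject's sampled primary tumour may therefore be non-avid.

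Three further points can be made for the plan. The SAP refers imaging detail to a separate document that is not at hand; if the core laboratory records 0 where no avid lesion is seen, the cut would act as the avidity call. That a measured SUVmean is seldom exactly 0 is an assumption here, not something the SAP says. And SUV-based positivity is not foreign to the plan, since a Phase II objective in Section 1.1.2 mentions assessment by SUV.

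The population and unit points stand, and they limit the claim. The appeal to a coding convention does not rescue the rule: Section 3.2.3 states a cut without stating the convention, and Section 3.2.4.1 would drop an unrecorded SUVmean rather than enter it as 0. Where the SAP wants zero substituted for an unreported value it says so, as for neutrophils in Appendix 1, item 14.

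**Conclusion.** The concern holds in limited form. A cut at SUVmean above 0 leaves the PET-negative row empty at subject level in treated subjects and in the 68Ga-OPS202 positive population. In all imaged subjects the row is empty or nearly so if any non-zero regional uptake counts as positive. It fills only if screen failures are included and their non-avid tumours are coded 0, or if a sampled primary tumour is itself non-avid and coded 0. The SAP fixes neither the population nor the coding. The cut also conflicts with the avid/non-avid definition in Sections 1.2 and 2.2.3.

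The consequence is small. The table is exploratory, descriptive and additional to correlations that use SUVmean as a continuous measure and do not depend on the cut. Section 5 reduces the outputs after premature closure to selected listings, none of which covers IHC or SUVmean, so no reported result of this study is affected under this version. What remains is a definition worth correcting before the wording is reused, for instance in another protocol under the Master Protocol that Section 1.2 describes. The kappa values are illustrations under assumed H-score shares, not predictions.

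**What to change.** In Section 3.2.3, replace the SUVmean cut for the 2×2 table with the central reader's avid or non-avid call for the lesion matched to the biopsied tissue. State that the table covers all subjects with both a screening biopsy and a 68Ga-OPS202 PET, including screen failures. Leave the Pearson and Spearman analyses of continuous SUVmean as they are.

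The cost is SAP wording. A central avidity read already exists for eligibility. Two practical conditions apply: the biopsied lesion must be identifiable on the PET, and the tissue of screen failures must have been stained. If either fails for some subjects, report how many are left out of the table.
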